At Visit 2, volunteers will arrive at the [REDACTED] on the evening of Day -1 (the day before dosing). Volunteers will be randomised to receive a single dose of AZD9668 or placebo on Day 1 (Visit 2) in a ratio of 6:2 (AZD9668:placebo) in each ethnic group. Volunteers will remain in the [REDACTED] for assessments until approximately 72 hours post dose (Day 4) and then can be discharged. Volunteers will return to the [REDACTED] on the evening of Day 6. On Day 7 (Visit 3), each volunteer will receive a second single dose. Volunteers will remain in the [REDACTED] for assessments until approximately 72 hours post dose (Day 10) and then can be discharged. Volunteers will return to the [REDACTED] on the evening of Day 12. Multiple doses will be administered twice daily on Days 13 to 18 (Visit 4), each dose administered 12 hours apart, and a final, single dose on the morning of Day 19. Volunteers will remain in the [REDACTED] for assessments until approximately 72 hours after this last dose (Day 22), when they can be discharged (at the Investigator's discretion). Volunteers will attend for a follow-up (Visit 5) at least 7 days (+2 days) after discharge from Visit 4.

Within each cohort, dose escalation will only proceed once dosing has been completed at the previous dose level, however, it is possible that multiple dose (cohort 1) and single dose 1 (cohort 2) may run in parallel.

Investigator /SRC's will review available data as described below for each cohort and as shown in Figure 1. For cohort 1, following completion of the first single dose level, the Investigator will review available safety data (blinded) to confirm that it is safe to proceed with the next single dose level. After the second single dose, a blinded Safety Review Committee (SRC) will meet to review the available safety data from single doses 1 and 2 to determine whether it is safe to proceed with the multiple dose in these individuals and the single dose 1 for cohort 2. The SRC will also review the PK data (up to 24 hours post dose as a minimum) from the single dose 1, and emerging data from the AstraZeneca Global SAD/MAD Study to confirm dose selection. Following the completion of the multiple dose, the SRC will review the available safety data from the multiple dose (cohort 1) and the PK data (up to 24 hours post dose as a minimum) from the first two single doses.

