For cohort 2 after completion of the first single dose level the SRC will meet to review safety data from the single dose 1 (cohort 2) and the PK data (up to 24 hours post dose) from the single doses in cohort 1 as a minimum. The SRC will then determine whether it is safe to proceed to single dose 2 (cohort 2) and use available PK data, and emerging data from the AstraZeneca Global SAD/MAD Study to confirm the dose. After single dose 2 (cohort 2) a SRC will meet to review the available safety data from single doses 1 and 2 (cohort 2) to determine whether it is safe to proceed to multiple dose (cohort 2) and use the PK data available from single dose 1 (cohort 2) and cohort 1 (both single and multiple doses), and emerging data from the AstraZeneca Global SAD/MAD Study to confirm the dose. The SRC will also meet following the completion of the multiple dose (cohort 2) to review safety data, and PK data if available, for internal information.

Note: All safety and PK data from the current study will be reviewed blinded.

Figure 1 Study flow chart

[figure not shown]

Table 1 Study plan

Assessment	Visit 1a	Visit 1b	Visit 2	Visit 3	Visit 4	Visit 5
		Day -21 to -1	Day 1	Day 7	Day 13 to 19	Day 29 (+2 days)
Informed consent / enrolment	X					
Genetic consent	X					
Inclusion/Exclusion criteria		X	X			
Demographics		X				
Medical and surgical history		X				
Concomitant medication		X	X	X	X	X
Physical examination (inc. height and weight)		X	X ^{1,2}			X ²
Alcohol and drugs of abuse screen		X	X	X ³	X ³	X ³
Hepatitis B&C and HIV screen		X				
Safety bloods and urinalysis		X	X ⁴	X ⁴	X ⁴	X
12-Lead ECG (paper)		X	X	X	X ⁵	X
12-Lead ECG (digital)			X ⁶	X ⁶	X ⁶	
Telemetry			X ⁷	X ⁷	X ⁷	
Sitting blood pressure and pulse		X	X ⁸	X ⁸	X ⁸	X
Pregnancy test		X ⁹				
Adverse events		X	X	X	X	X
Randomisation			X			
AZD9668 or placebo administration			X	X	X	
Plasma PK profile			X ¹⁰	X ¹⁰	X ¹⁰	
Full urine collection (PK)			X ¹¹	X ¹¹	X ¹¹	
PD blood sample			X ¹²	X ¹²	X ¹²	
PGx blood sample			X ¹³			

¹ Abbreviated physical examination only.

² Weight only will be measured at this visit.

³ To be performed when volunteer returns to the [REDACTED] between study visits.

⁴ Pre-dose in each dosing period.

⁵ Paper ECGs recorded at the timepoints shown in Table 2, and at 48 and 72 hrs post dose at Visits 2, 3 and 4. If dECGs are to be performed each should be preceded by a paper ECG recording.

⁶ Digital ECGs (if required) will be performed at the times shown in Table 2.

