3.1.1.3 Stopping criteria for dose escalation during the multiple dose phase

Escalation to the next dose level will not occur if any of the following criteria are met with the previous dose levels:

- Two or more volunteers on active treatment are discontinued because of either an ALT/AST level $\geq 3 \times ULN$ or any pattern of LFT abnormalities giving cause for concern.
- Evidence of haemolysis as evidenced by the following in two or more volunteers on active treatment.
 - Reticulocyte count of over 5%, and,

At least two of the following:

- A drop in haemoglobin below 10.5 g/dL.
 - Decrease of 25% in haptoglobin. (The value post-dose to be compared with the average of two pre-dose values. The value should also be 15% below LLN).
 - Increase of 25% in unconjugated bilirubin or LDH. (The value post-dose to be compared with the average of two pre-dose values. The value should also be 15% above ULN).
- A platelet count of below $80,000 \times 10^9/L$ confirmed by a repeat test (in the absence of obvious platelet clumping in a peripheral blood film) in two or more volunteers on active treatment.
 - A QTcF >500 ms in two or more volunteers on active substance (QT interval corrected for heart rate by Fridericia method) or a QTcF prolongation >60 ms on average, sustained for more than 30 minutes, ie, present on two contiguous timepoints, in two or more volunteers on active substance based on the results of the continuous readings compared to baseline.
 - Any general safety finding that in the opinion of the Investigator gives cause for concern.
 - Data indicate that at the next proposed dose the geometric mean steady state exposure ($C_{\max,ss}$ or $AUC_{(0-24),ss}$) will exceed 18 $\mu M.h$ and 2.5 μM , respectively.

Dosing in an individual volunteer may be discontinued in the multiple dose phase of the study (see Section 3.3.5.1 for criteria).

The stopping criteria refer to all volunteers at a specific dose level. In the event of the need to unblind the data for a given volunteer, or a given cohort, the study design will revert to a single blind study for that volunteer or cohort.

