3.3.5 Discontinuation of subjects from treatment or assessment

3.3.5.1 Criteria for discontinuation

Volunteers may be discontinued from study treatment and assessments at any time. Specific reasons for discontinuing a volunteer from this study are:

- Voluntary discontinuation by the volunteer, who is at any time free to discontinue his/her participation in the study without prejudice to further treatment.
- Safety reasons as judged by the Investigator and/or AstraZeneca.
- Severe non-compliance to protocol as judged by the Investigator and/or AstraZeneca.

- Incorrect enrolment ie, the volunteer does not meet the required inclusion/exclusion criteria for the study.
- Volunteer lost to follow-up.

Dosing will be discontinued in the multiple dosing period (ie, during Visit 4) if the criteria below are met:

- An ALT/AST level ≥ 3 x ULN or any pattern of LFT abnormalities giving cause for concern.
- Evidence of haemolysis as evidenced by the following in two or more volunteers on active treatment.
 - Reticulocyte count of over 5%, and,

At least two of the following:

- A drop in haemoglobin below 10.5 g/dL.
- Decrease of 25% in haptoglobin. (The value post-dose to be compared with the average of two pre-dose values. The value should also be 15% below LLN).
- Increase of 25% in unconjugated bilirubin or LDH. (The value post dose to be compared with the average of two pre dose values. The value should also be 15% above ULN).
- A platelet count of below $80,000 \times 10^9/L$ confirmed by a repeat test (in the absence of obvious platelet clumping in a peripheral blood film) in two or more volunteers on active treatment.
- A QTcF >500 ms in two or more volunteers on active substance (QT interval corrected for heart rate by Fridericia method) or a QTcF prolongation >60 ms on average, sustained for more than 30 minutes, ie, present on two contiguous timepoints, in two or more volunteers on active substance based on the results of the continuous readings compared to baseline.
- Any general safety finding that in the opinion of the Investigator or SRC gives cause for concern.

Specific reasons for discontinuing a volunteer from the genetic research when genetics is a secondary objective of the study are:

- Withdrawal of consent for genetic research. A volunteer may withdraw from this genetic research at any time, independent of any decision concerning participation

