4.4 Safety measurements

4.4.1 Laboratory safety measurements

Blood and urine samples for the determination of clinical chemistry, haematology and urinalysis parameters will be taken at the times given in the study plan (Table 1). The date of collection will be recorded on the appropriate CRF page.

Samples will be collected in the following tubes and at the volumes specified:

Clinical chemistry – 8.5 mL serum separation tube (SST) vacutainer.

Haematology – 3 mL EDTA vacutainer.

Urinalysis – 20 mL universal tube.

The following laboratory variables will be measured:

Clinical Chemistry

Creatinine	Triglycerides
Total, conjugated, and unconjugated bilirubin	Urea
Alkaline phosphatase	Gamma Glutamyltransferase (GGT)
Aspartate aminotransferase (AST)	Creatinine phosphokinase (CPK) ^a
Alanine aminotransferase (ALT)	Lactate dehydrogenase (LDH)
Albumin	Glucose (fasting)
Potassium	Follicle stimulating hormone (FSH) ^c
Calcium, total	Haptoglobin
Sodium	
High sensitivity C-reactive protein (hsCRP)	
Cholesterol	

Haematology

Haemoglobin
Leukocyte count
Red cell count (RBC)
Haematocrit
Mean cell volume (MCV)
Mean cell haemoglobin (MCH)
Mean cell haemoglobin concentration (MCHC)
Leukocyte differential count (absolute)
Platelet count
Reticulocyte count

Urinalysis

Blood
Protein
Ketones
Glucose
Bilirubin
Urobilinogen

Virology ^b

Hepatitis B surface antigen
Hepatitis C antibodies
HIV 1 and 2 antibodies

^a If elevated >3, P-CPK-MB will be analysed (will not be data-based).

^b Included at Visit 1b only.

^c Only analysed in female volunteers. Included at Visit 1b only.

Urine will be tested for the following drugs of abuse:

Methadone, benzodiazepines, cocaine, amphetamines, tetrahydrocannabinoids (THC), morphine, methamphetamines (ecstasy), barbiturates, phencyclidine (PCP) and tricyclic antidepressants (TCA).

If a volunteer tests positive for drugs of abuse they will be excluded from entering, or continuing in, the study.

Female volunteers must give a sample of the first urine passed at Visit 1b for a pregnancy test to be performed. It is important to check that volunteers are not pregnant when they enter the study but it is unnecessary to re-test during the study as they have already been defined as 'non-childbearing potential'.

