4.6 Volume of blood sampling

The total volume of blood that will be drawn from each volunteer in this study is shown in Table 6.

Table 6 Maximum volume of blood to be drawn from each volunteer

Assessment		Sample volume (mL)	n of samples	Total volume (mL)
PD analysis: zymosan stimulated NE activity		4.5	11	49.5
PK analysis		4.0	65	260.0
Pharmacogenetics ^a		10.0	1	10.0
Safety:	Clinical chemistry	8.5	5	42.5
	FSH (Visit 1b)	8.5	1	8.5
	Haematology	3.0	5	15.0
Virology:	Hepatitis B and C and HIV	8.5	1	8.5
Cannula discard (approx.)		1	65	65.0
Total				459.0

^a If consent has been obtained

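### No safety laboratory sample is scheduled during the 13 multiple doses or before Day 29, although dosing must stop in that period on laboratory values

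*Protocol*

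**What the plan says.** **Timing of samples.** Section 4.4.1 says that chemistry, haematology and urinalysis samples "will be taken at the times given in the study plan (Table 1"). Table 1 marks safety bloods and urinalysis at Visits 1b, 2, 3, 4 and 5. For Visits 2, 3 and 4, footnote 4 restricts them to "Pre-dose in each dosing period". Table 6 (Section 4.6), headed "Maximum volume of blood to be drawn from each volunteer", allows five chemistry and five haematology samples.

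**Follow-up.** Section 3.1: "Volunteers will attend for a follow-up (Visit 5) at least 7 days (+2 days) after discharge from Visit 4". Discharge is on Day 22, and Table 1 puts Visit 5 at Day 29 (+2 days).

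**Individual stopping rule.** Section 3.3.5.1: "Dosing will be discontinued in the multiple dosing period (ie, during Visit 4) if the criteria below are met". The list includes ALT/AST at or above 3 x ULN or a worrying LFT pattern, haemolysis markers, and a confirmed low platelet count. QTcF and general safety criteria are listed as well.

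**Escalation rule.** The liver criterion in Section 3.1.1.3 begins "Two or more volunteers on active treatment are discontinued because of either an ALT/AST level". The haemolysis and platelet criteria there are not tied to discontinuation, and there is a general criterion: "Any general safety finding that in the opinion of the Investigator gives cause for concern".

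**The concern.** A rule that dosing must stop on a laboratory value is only as good as the sampling that could produce the value. The haptoglobin and bilirubin/LDH criteria in Section 3.3.5.1 compare a post-dose value with the average of two pre-dose values, so the rule itself assumes that post-dose samples exist. None is scheduled while the volunteer is taking the twice-daily regimen.

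The synopsis names chemistry and haematology among the primary safety variables for multiple dosing. The preclinical findings in Sections 1.1 and 3.2.2 are mild and occurred at high doses, but they are laboratory findings: haematological changes in dogs (without bone-marrow pathology) and slightly raised creatinine on repeat dosing. Symptoms may not reveal such changes. One that arose after the Day 13 sample and resolved before Day 29 would be missed unless someone ordered an unscheduled test. One that persisted would be seen only after all doses had been given.

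The schedule is fixed in the protocol, so a statistical analysis plan could not repair this.

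**Working it through.** **1. Reproduce the protocol's own counts.**
- Safety sets: Visits 1b, 2, 3, 4 and 5 give 5, matching the 5 chemistry and 5 haematology samples in Table 6.
- PK draws in Table 3: Day 1 (15) + Day 7 (15) + Day 13 (13) + Days 14 and 15 (2) + Days 16 and 17 (4) + Day 18 (1) + Day 19 (15) = 65, matching Table 6.
- Volume: 49.5 + 260.0 + 10.0 + 42.5 + 8.5 + 15.0 + 8.5 + 65.0 = 459.0 mL, matching Table 6.

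**2. Could footnote 4 mean pre-dose on every dosing day?** No. Section 3.3.5.1 treats Visit 4 as a single multiple dosing period. Five samples in total also leave only one for Visit 4, which must precede the first Day 13 dose.

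**3. Doses and gaps.**
- Multiple doses: 6 days x 2 + 1 on Day 19 = 13.
- Scheduled laboratory sets after the first of these and before Visit 5: 0.
- Day 13 pre-dose to Visit 5: 29 - 13 = 16 days, or 31 - 13 = 18 with the +2 window.
- Last dose to Visit 5: 29 - 19 = 10 days, or 31 - 19 = 12.

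**4. Rules against scheduled data.**

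| Rule | Scheduled value during dosing | What a Day 29 value can do |
|---|---|---|
| 3.3.5.1 ALT/AST or LFT pattern | None | Nothing; dosing has ended |
| 3.3.5.1 haemolysis | None | Nothing; dosing has ended |
| 3.3.5.1 platelets | None | Nothing; dosing has ended |
| 3.1.1.3 liver (counts discontinued volunteers) | None | Cannot cause a discontinuation, so cannot add to the count |
| 3.1.1.3 haemolysis, platelets, general safety | None from the laboratory | Can still block escalation |

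**5. Secondary and conditional: overlap between cohorts.** Section 3.1 allows cohort 1's multiple dosing and cohort 2's first single dose to run in parallel. Assume cohort 2 Day 1 falls on cohort 1 Day 13.
- Nominal study days: cohort 2's multiple dosing starts on cohort 1 Day 13 + 12 = 25, which is 29 - 25 = 4 to 31 - 25 = 6 days before cohort 1's first laboratory value after multiple dosing.
- 7-day separations: the start is Day 13 + 14 = 27, which is 2 to 4 days before that value.

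**The case against.** The sampling schedule is hard to dispute. The case on the other side concerns how much it matters, and parts of it stand.

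- **Exposure is bounded.** Single doses up to 150 mg had been given in the global study, with 36 subjects on active drug across dose levels, no serious adverse events and no event judged causally related (Section 3.2.1). The 140 mg daily cap lies below that single dose, and predicted steady-state exposure is limited to 2.5 μM and 18 μM·h. The only human multiple dosing cited is 30 mg daily, so the cap is 140/30 = 4.7 times higher, but that was an early snapshot and doses here are chosen on emerging data. These limits lower the expected hazard; they do not supply a laboratory value.
- **Other observation continues.** Volunteers are resident from Day 12 to Day 22, adverse events are collected throughout, and ECGs, vital signs and telemetry are scheduled. Unscheduled tests are not barred, and the Investigator may stop dosing on any safety ground. All true, but an unscheduled test needs a prompt, which a silent change does not give.
- **Visit 5 exists.** A persistent change would be found there. The gap therefore concerns silent, transient changes and the ability to stop in time.
- **The cohort overlap is uncertain.** It depends on an assumed start date, and the flow chart (Figure 1) is not available in the text reviewed. The safety review committee also plans to review cohort 1's multiple-dose safety data after that dosing ends, and uses available cohort 1 multiple-dose PK data before cohort 2's multiple dose. The start could be later than calculated. The main point does not need the overlap.

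**Conclusion.** The concern holds and should be corrected before multiple dosing starts. As written, none of the liver, haemolysis and platelet criteria for stopping during Visit 4 can be evaluated from a scheduled on-treatment sample. They can operate only through unscheduled tests or a late Day 13 pre-dose result. The liver criterion for escalation inherits the same weakness because it counts discontinuations. The QTcF and general safety criteria are unaffected.

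The conclusion rests on reading footnote 4 as one sample per visit, which Table 6 and Section 3.3.5.1 both support. It does not rest on any assumed event rate or on the cohort overlap.

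**What to change.** Amend Table 1 footnote 4 and Table 6 to add two chemistry and haematology sets at existing PK draws, for example:

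- **Day 16 pre-dose:** 3 x 2 = 6 multiple doses given, 7 remaining. If results are back within 24 hours (an assumption), both Day 16 doses will have been taken and 13 - 8 = 5 doses can still be withheld.
- **Day 19 pre-dose:** 12 doses given. This is mainly an end-of-exposure value for the summary and the committee; with a 24-hour turnaround it would not prevent the last dose.

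The clinical team should set the exact times and a required turnaround. Require the safety review committee to have cohort 1's on-treatment results before cohort 2's multiple dosing.

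**Cost.** A protocol amendment and 2 x 32 = 64 laboratory sets if 32 volunteers are enrolled. Each set is 8.5 + 3.0 = 11.5 mL, so 23.0 mL per volunteer. No extra venepuncture or cannula discard is needed, because both draws are already in Table 3 and Section 4 already ranks safety bloods alongside PK samples. Both are fasted under Section 3.4.2, as the glucose test requires.

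**Blood volume.** The maximum becomes 459.0 + 23.0 = 482.0 mL, for a woman giving the pharmacogenetic sample. Against the 500 mL limit in exclusion criterion 10 this leaves 18.0 mL: one 11.5 mL repeat set, with 6.5 mL over. The drawback is that blood donated earlier in the 90-day window counts towards the same limit.

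**Optional.** A third set on Days 20 to 22, at a PK draw already planned, would cover the period just after the last dose. It would bring the maximum to 493.5 mL and use the room otherwise left for a repeat set.

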3.1.1 Stopping criteria for dose escalation

3.1.1.1 Safety Review Committee

Within each cohort dose escalation will only proceed once dosing has been completed at the previous dose level, however, it is possible that multiple dose (cohort 1) and single dose 1 (cohort 2) may run in parallel. For cohort 1, following completion of the first single dose level, the Investigator will review available safety data (blinded) to confirm that it is safe to proceed with the next single dose level. After the second single dose, a blinded Safety Review Committee (SRC) will meet to review the available safety data from single doses 1 and 2 to determine whether it is safe to proceed with the multiple dose in these individuals and the single dose 1 for cohort 2. The SRC will also review the PK data (up to 24 hours post dose as a minimum) from the single dose 1, and emerging data from the AstraZeneca Global SAD/MAD Study to confirm dose selection. Following the completion of the multiple dose, the SRC will review the available safety data from the multiple dose and the PK data (up to 24 hours post dose as a minimum) from the first two single doses.

For cohort 2 after completion of the first single dose level the SRC will meet to review safety data from the single dose 1 (cohort 2) and the PK data (up to 24 hours post dose) from the single doses in cohort 1 as a minimum. The SRC will then determine whether it is safe to proceed to single dose 2 (cohort 2) and use available PK data, and emerging data from the AstraZeneca Global SAD/MAD Study to confirm the dose. After single dose 2 (cohort 2) a SRC will meet to review the available safety data from single doses 1 and 2 (cohort 2) to determine whether it is safe to proceed to multiple dose (cohort 2) and use the PK data available from single dose 1 (cohort 2) and cohort 1 (both single and multiple doses), and emerging data from the AstraZeneca Global SAD/MAD Study to confirm the dose. The SRC will also meet following the completion of the multiple dose (cohort 2) to review safety data, and PK data if available, for internal information.

Note: All safety and PK data from the current study will be reviewed blinded.

The SRC will be chaired by an AstraZeneca Physician and will comprise the following individuals, as a minimum:

- AstraZeneca study team physician, or nominated deputy.
- AstraZeneca drug safety physician, or nominated deputy.
- AstraZeneca study team pharmacokineticist, or nominated deputy.
- Principal Investigator, or nominated deputy.
- [REDACTED] medical monitor, or nominated deputy
- [REDACTED] study team statistician, or nominated deputy.

The safety review will lead to one of five possible outcomes:

- Escalate to a higher dose.
- Repeat dose level.
- Stop escalation and investigate lower dose(s).
- End overall study.
- End part of study.

Volunteers may be withdrawn from the study at any time at the discretion of the Principal Investigator. Specific reasons for discontinuing a volunteer from the study are listed in Section 3.3.5.

Where there is no consensus between the Principal Investigator and the SRC on dose escalation, the Principal Investigator will take the final decision in the interest of safety of the volunteers.

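### Cohort 2 multiple dosing is not made to wait for cohort 1 multiple-dose safety results, so it can start before any scheduled post-dose blood test from cohort 1

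*Protocol*

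**What the plan says.** Each cohort receives two single doses and one multiple-dose level. The step from cohort 1 to cohort 2 is therefore the only multiple-dose escalation that Section 3.1.1.3 can govern.

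For that step, Sections 3.1 and 3.1.1.1 have the SRC "review the available safety data from single doses 1 and 2 (cohort 2) to determine whether it is safe to proceed to multiple dose" in cohort 2. To confirm the dose, the SRC is to "use the PK data available from single dose 1 (cohort 2) and cohort 1 (both single and multiple doses"), together with emerging data from the Global SAD/MAD study. So cohort 1 multiple-dose PK is named and cohort 1 multiple-dose safety is not.

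The SRC does review available cohort 1 multiple-dose safety data once that dosing is complete, but the text does not say that cohort 2 multiple dosing waits for this review. The rule that one dose level must be completed before the next applies within a cohort. Across cohorts, "it is possible that multiple dose (cohort 1) and single dose 1 (cohort 2) may run in parallel", and a single SRC meeting can release both.

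Table 1, footnote 4, times the safety bloods at Visits 2, 3 and 4 as "Pre-dose in each dosing period". The next scheduled bloods are at the "follow-up (Visit 5) at least 7 days (+2 days) after discharge from Visit 4", which Table 1 places on Day 29 (+2 days).

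**The concern.** Section 3.1.1.3 forbids escalation if its criteria were met at earlier dose levels. It does not require the data behind those criteria to exist first. The haemolysis criterion needs a reticulocyte count plus haemoglobin, haptoglobin, and bilirubin or LDH values; the platelet criterion needs a platelet count. If no blood has been drawn since cohort 1 began multiple dosing, neither criterion can be met, whatever has happened to the volunteers. The rule would then permit escalation because nothing had been measured.

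Haematological change is one of the preclinical findings that Section 3.2.2 treats as possibly relevant to humans. The only multiple-dose experience from the Global study described in the protocol is 30 mg daily, against a ceiling here of 140 mg daily (140/30 = 4.7). That ratio compares a ceiling with what had been given when the protocol was written. It is not the size of the cohort 1 to cohort 2 step, which is not fixed.

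**Working it through.** **Does any scheduled laboratory draw fall between Visit 4 pre-dose and Visit 5?** Table 1 with footnote 4 gives one draw at each of Visits 1b, 2 (pre-dose), 3 (pre-dose), 4 (pre-dose) and 5, which is five. Table 6 agrees:

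- clinical chemistry: 5 × 8.5 mL = 42.5 mL
- haematology: 5 × 3.0 mL = 15.0 mL
- full table: 49.5 + 260.0 + 10.0 + 42.5 + 8.5 + 15.0 + 8.5 + 65.0 = 459.0 mL, the stated total

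The count leaves no room for a sixth draw, so none is scheduled between Day 13 pre-dose and Visit 5.

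**When can cohort 2 multiple dosing start, on the cohort 1 calendar?** Let *s* be the cohort 1 day on which cohort 2 takes single dose 1. Overlap with cohort 1 multiple dosing means *s* = 13 to 19. Let *k* be the days from one dosing period to the next. Then:

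- first cohort 2 multiple dose = *s* + 2*k*
- gap = max(0, 29 − (*s* + 2*k*)) to max(0, 31 − (*s* + 2*k*)) days
- cohort 2 doses given before Visit 5 = 2 × gap, out of 6 × 2 + 1 = 13

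Three values of *k* are needed because Section 3.1 asks for a washout of at least 7 days while Days 1, 7 and 13 are 6 days apart: *k* = 6 (calendar as written), 7 (7 days dose to dose) or 8 (seven full dose-free days).

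| *s* | *k* = 6: start day, gap | *k* = 7: start day, gap | *k* = 8: start day, gap |
|---|---|---|---|
| 13 | 25, 4–6 | 27, 2–4 | 29, 0–2 |
| 14 | 26, 3–5 | 28, 1–3 | 30, 0–1 |
| 15 | 27, 2–4 | 29, 0–2 | 31, 0 |
| 16 | 28, 1–3 | 30, 0–1 | 32, 0 |
| 17 | 29, 0–2 | 31, 0 | 33, 0 |
| 18 | 30, 0–1 | 32, 0 | 34, 0 |
| 19 | 31, 0 | 33, 0 | 35, 0 |

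At *s* = 13, cohort 2 doses given before Visit 5 are 8 to 12 (*k* = 6), 4 to 8 (*k* = 7) or 0 to 4 (*k* = 8).

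If Visit 5 falls on Day 29, a gap arises only for *s* = 13 to 16 with *k* = 6, or *s* = 13 to 14 with *k* = 7, and never with *k* = 8. Other starts give at most 2 days, and only if the +2 window is used. Without overlap the earliest case is *s* = 20, *k* = 6: 20 + 12 = Day 32, after the latest Visit 5 on Day 31, so there is no gap.

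**What is already in hand by then?** Adverse events, ECGs, telemetry and vital signs from cohort 1 could all be available by Day 22, before the earliest start on Day 25. The liver criterion in Section 3.1.1.3 counts discontinuations and is not part of this point. What remains unmeasured by scheduled samples is haemolysis and platelets.

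**The case against.** The strongest counter-arguments are these.

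- **Figure 1 is not available here.** Section 3.1 says the Investigator and SRC "will review available data as described below for each cohort and as shown in Figure 1", and the figure may fix an order of meetings that the text does not. This stands as a limit. Section 3.1.1.1 as written still does not supply the order.
- **The review will happen in time anyway.** Cohort 1 dosing ends on Day 19 and the earliest cohort 2 multiple dose is Day 25, so the planned SRC review of cohort 1 has a natural slot. Multiple doses are also to be chosen from emerging study data. Both are true, but a review on, say, Day 23 would contain no scheduled post-dose laboratory value. Emerging data carries no minimum content, although the same sections do set one for some PK data.
- **Waiting for cohort 1 multiple-dose PK may use up the gap.** Day 19 sampling runs to 72 hours, Day 22, and assay time follows. This is plausible, but the text asks only for the PK that is available, and Day 13 PK might suffice.
- **Several conditions must coincide.** Early overlap is allowed but not required, and the largest figure depends on the 6-day calendar that conflicts with the stated washout. This stands, and it is why the size is given as a range.
- **Other safeguards exist.** Dose and exposure are capped, the Investigator can stop for any safety concern, and unscheduled tests are possible. The dog findings were mild, seen at high doses, and without marrow pathology. These lower the risk, but none of them requires a blood result before escalation.

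**Conclusion.** The concern holds, and the plan should be changed. Followed to the letter, the protocol allows its only multiple-dose escalation while two of its own stopping criteria are unmeasured by scheduled samples.

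The exposure is narrow: at most 4 to 6 days (8 to 12 of 13 doses) under the earliest overlap on the written calendar, falling to nothing with late overlap, longer spacing or no overlap. The figures assume that all cohort 1 volunteers share one calendar, that no unscheduled laboratory tests are done and that Figure 1 adds no further condition. Each day of stagger among cohort 1 volunteers adds one day to the gap for the last of them. Confidence is medium, mainly because Figure 1 could not be seen.

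**What to change.** Add one sentence to Sections 3.1 and 3.1.1.1: multiple dosing in cohort 2 will not begin until the SRC has reviewed cohort 1 multiple-dose safety data, including at least one safety laboratory result taken after multiple dosing (Visit 5 under the current schedule).

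This uses the existing committee and samples. With early overlap it means a hold of about 1 to 6 days (0 to 2 days with seven full dose-free days), plus laboratory turnaround and SRC scheduling, neither of which the protocol states. The hold is longer if cohort 1 volunteers are staggered, which can happen because the ethnic groups run in parallel only where practicable. A low platelet count would also need the repeat test that the criterion already demands. Without overlap there is no delay.

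One limit remains: Visit 5 falls about 10 days after the last dose (29 − 19 = 10), so it is a late check. A change that resolved quickly could be missed.
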